8.6.2. Physical Examinations

Physical examination results of Normal, Abnormal and Not Done will be included in listings for subjects in the SfAS.

8.6.3. Otoscopic Examinations

Otoscopic examinations including external inspection and internal ear examination, will be performed at the Screening/Start of Lead-In, End of Lead-In/Treatment, Day 30, Day 60, Day 90, Day 180, and Day 270 visits. Otoscopic examination data will be summarized descriptively by visit for treated ears by treatment group for subjects in the SfAS. An otoscopic findings shift table for treated ears from baseline to post-baseline visits will also be produced by treatment group. Unscheduled visit and early termination visit data will not be mapped to scheduled visits per Section 7.1.2. Unscheduled visit and early termination visit data will be excluded from summary tables and included in listings.

Otoscopic examination data for both treated and untreated ears, scheduled and unscheduled, will be presented in a data listing for subjects in the SfAS.

8.6.4. Tympanometry

Pa	ge 46 of 64
Version Date: 2023-01-19	Version: 2.0

Tympanometry will be performed at the Screening/Start of Lead-In, End of Lead-In/Treatment, Day 30, Day 60, Day 90, Day 180, and Day 270 visits. Tympanometry data including type of tympanogram, ear canal volume, peak admittance, and peak pressure will be summarized descriptively for treated ears by visit and treatment group for subjects in the SfAS. A tympanogram classification shift table for treated ears from baseline to postbaseline visits will also be produced by treatment group. Unscheduled visit and early termination visit data will not be mapped to scheduled visits per Section 7.1.2. Unscheduled visit and early termination visit data will be excluded from summary tables and included in listings.

All tympanogram data for both treated and untreated ears, scheduled and unscheduled, will be presented in a data listing for subjects in the SfAS.

8.6.5. Columbia-Suicide Severity Rating Scale Assessments

The C-SSRS will be completed at the End of Lead-In/Treatment (Baseline/Screening version), Day 30, Day 60, Day 90, Day 180, and Day 270 visits. All suicidal ideation and behavioral variables collected will be summarized descriptively for each visit by treatment group for subjects in the SfAS.

All C-SSRS data, scheduled and unscheduled, will be included in data listings for all subjects in the SfAS.

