### **13.2.6 Columbia Suicide Severity Rating Scale (C-SSRS)**

This scale is used to determine if any suicide ideation or intention is present (Posner et al 2011). The questionnaire is read aloud to the subject and responses are recorded by the trained staff member. If any ideation or intention is present, the Investigator will interview the subject and have them follow up with their primary healthcare provider. The C-SSRS will be completed at Visit 3 (Baseline/Screening version), Visit 4, Visit 5, Visit 6, Visit 7, and Visit 8 (Since Last Visit version).

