- For all efficacy endpoints, including word recognition in quiet (Maryland Consonant-Nucleus-Consonant [CNC] and W-22) and words in noise (WIN), baseline values for analysis will be defined by ear as the average across the pre-treatment timepoints (Lead-in and Day 1) for left and right ears separately. For the analyses of improvement from baseline above upper confidence limits, either per Carney-Schlauch (2007) or Thornton-Raffin (1978), the rounded up average will be used for conservative approach. Left and right ears will be mapped to treated and untreated for analysis.
- For all safety endpoints and other analyses, baseline will be the last non-missing value before study drug administration.
- For efficacy analyses, Day 90 values will be based on the scheduled Day 90 nominal case report form (CRF) recorded visit. If no scheduled visit data is available for the nominal day 90 CRF recorded visits, the non-missing data in either ear from an early termination or unscheduled assessment performed closest to the target day will be used.

- All endpoints which reference a change in percentage of recognized words are calculated as and should be interpreted as a linear change (i.e., observed baseline) and not a relative change (i.e. (observed baseline)/baseline x 100).
- For all shift from baseline analyses, percentages will be based on the number of subjects in each category at baseline and the post-baseline visit.
- All analysis will be performed using the SAS System version 9.4 or higher.

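### Change in C-SSRS is a named safety endpoint, but the SAP plans no C-SSRS-based, per-subject count of new or worsened ideation or behavior after dosing

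*SAP*

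**What the plan says.** The safety endpoints in the protocol (Synopsis and Section 9) are adverse events and changes in three assessments: otoscopy, tympanometry and C-SSRS.

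For C-SSRS, SAP 8.6.5 sets the schedule: "The C-SSRS will be completed at the End of Lead-In/Treatment (Baseline/Screening version), Day 30, Day 60, Day 90, Day 180, and Day 270 visits". It then plans two outputs:

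- a summary: "All suicidal ideation and behavioral variables collected will be summarized descriptively for each visit by treatment group for subjects in the SfAS";
- a listing: "All C-SSRS data, scheduled and unscheduled, will be included in data listings for all subjects in the SfAS".

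For the other two assessments the SAP goes further. In 8.6.3: "An otoscopic findings shift table for treated ears from baseline to post-baseline visits will also be produced by treatment group". In 8.6.4: "A tympanogram classification shift table for treated ears from baseline to postbaseline visits will also be produced by treatment group".

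A baseline rule that would serve C-SSRS already exists in SAP Section 3: "For all safety endpoints and other analyses, baseline will be the last non-missing value before study drug administration". Section 8.6.5 does not use it.

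Protocol 13.2.6 assigns the Baseline/Screening form to Visit 3 and the Since Last Visit form to Visits 4 to 8. SAP 8.6.5 names only the first of these. SAP Section 11 declares no departure from the analyses planned in the protocol.

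**The concern.** Change is a property of a subject: where that subject stood before dosing and where the same subject stood afterwards. Totals at each visit are marginal counts. They do not link a post-dose positive to the subject's own Visit 3 result, and they do not say whether positives at successive visits are the same people.

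The question a safety reader will ask is how many subjects in each arm had ideation or behavior after the injection that was new or worse than before. As planned, no C-SSRS table answers it, and the SAP does not define what would count as new or worse. If positives on FX-322 were mostly new and those on placebo mostly long-standing, the two arms could show identical tables.

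**Working it through.** The documents give no C-SSRS rate and no C-SSRS figure to reproduce. All counts of positive subjects below are assumed. The 62 per arm is the planned number randomized (Protocol Table 1).

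**1. What is planned for each change endpoint**

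| Endpoint (Protocol Section 9) | By-visit summary | Shift from baseline | Once-per-subject post-dose count |
|---|---|---|---|
| Otoscopy (SAP 8.6.3) | yes | yes | no |
| Tympanometry (SAP 8.6.4) | yes | yes | no |
| C-SSRS (SAP 8.6.5) | yes | no | no |

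**2. Two histories, one table**

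The pre-dose visit is one of the summarized visits, so a fair example must give both histories the same Visit 3 count.

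| | Visit 3 | Day 30 | Day 60 | Day 90 | New after dosing |
|---|---|---|---|---|---|
| History 1: subject A positive throughout | A | A | A | A | 0/62 |
| History 2: A remits; B, C and D each positive once | A | B | C | D | 3/62 = 4.8% |
| Planned table, either history | 1/62 | 1/62 | 1/62 | 1/62 | not shown |

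Each cell of the planned table is 1/62 = 1.6%. The number with any post-dose positive is 1/62 (1.6%) in History 1 and 3/62 (4.8%) in History 2.

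**3. General bounds**

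- With post-dose counts c1 to ck, the number of different positive subjects lies between max(c) and the smaller of 62 and sum(c). Two positives at each of five post-dose visits fit 2 to 10 subjects, that is 2/62 = 3.2% to 10/62 = 16.1%.
- With b positive at Visit 3 and k at a later visit, new cases at that visit lie between max(0, k − b) and k. With b = 6 and k = 4 that is 0 to 4.

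**4. Recall intervals**

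From scheduled Days 1, 30, 60, 90, 180 and 270, the Since Last Visit intervals are 29, 30, 30, 90 and 90 days. With the visit windows (±5 days to Day 90, ±7 days after) they range over 24–34, 20–40, 20–40, 78–102 and 76–104 days.

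Assume a constant 30-day probability m of a positive report. Over 90 days it becomes 1 − (1 − m)^3:

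- m = 1%: 2.97%
- m = 2%: 5.88%
- m = 5%: 14.26%

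Later visit rows can therefore be nearly three times the earlier ones with no change in risk. This limits reading down the table. It does not affect FX-322 against placebo within a row, because both arms have the same form and schedule.

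**5. Unscheduled and early-termination records**

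The schedule allows C-SSRS at unscheduled visits. SAP 7.1.2 lists unscheduled visits without displaying them separately in by-visit summaries. SAP 8.6.3 and 8.6.4 state how unscheduled and early-termination data are treated in their tables; 8.6.5 does not. A positive record from such a visit may therefore reach only the listing.

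**The case against.** The case on the other side has real force.

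- **The data are not lost.** Post-dose ideation and behavior are counted at each visit by arm, Visit 3 is one of the rows, and every record is listed. This stands. A reader might infer that post-dose suicidality is never counted or that the trial would have no C-SSRS result; the documents support neither. What is missing is the within-subject summary and a rule set in advance for what is new or worse. Counting by hand from a listing does not supply that rule.
- **Adverse event tables may catch cases.** Protocol 11.1 has new clinically relevant findings reported as adverse events, and SAP 8.3 tabulates events that start or worsen on or after dosing. This stands in part. Protocol 13.2.6 answers a positive response with an interview and referral but does not tie it to an adverse event record, and clinical relevance is a judgment. The route is possible, not assured.
- **The SAP follows the protocol's analysis text.** The Synopsis promises changes from baseline or shift tables for audiology, tympanometry and otologic data, without naming C-SSRS, and Protocol 15.6 promises only descriptive statistics for questionnaire responses. This is correct. The tension is with the endpoint list. A shift table is itself descriptive, so adding one contradicts nothing.
- **Table specifications are in separate documents (SAP Section 1).** They might add a row for any post-dose event, but they cannot be assumed to supply a derivation that the SAP does not define.
- **The two forms weaken any comparison with Visit 3.** This stands and limits the shift table proposed here. A reader might also infer that the change of form would make follow-up look like improvement. That depends on the look-back period of the Baseline/Screening form, which the documents do not give, so it is not claimed.

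**Conclusion.** The point holds in a limited form. Change in C-SSRS is a stated safety endpoint, and the plan as written yields no summary of within-subject change and no once-per-subject count of new or worsened ideation or behavior after dosing. In the example, the planned table is the same whether new cases are 0/62 or 3/62 (4.8%).

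The size rests on assumed counts, and the true rates are unknown. The structural point needs no such assumption: marginal counts alone do not generally determine within-subject change. No test, power calculation or decision rule depends on C-SSRS, and the efficacy conclusions are untouched. It is a worthwhile correction to a safety summary and does not threaten the trial. A once-per-subject count compared between arms remains valid despite the two forms, because both arms are assessed in the same way.

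**What to change.** Add to SAP 8.6.5, by treatment group in the SfAS:

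1. The number and percentage of subjects with any post-dose ideation or behavior, and the number and percentage whose post-dose category is worse than at Visit 3. Count each subject once, use all post-dose records including unscheduled and early-termination ones, and report through Day 90 and through Day 270.
2. A shift table from the Visit 3 category (none, ideation, behavior) to the worst post-dose category.
3. A footnote saying that Visit 3 uses the Baseline/Screening form and later visits the Since Last Visit form, with recall intervals of about 30 to 90 days. Comparison with baseline is therefore limited, and the comparison between arms is the main reading.

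Keep the by-visit summary and the listing.

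The cost is one or two descriptive tables from data already collected, with a change to SAP wording only. Two limits remain: the baseline comparison is imperfect across forms, and worsening within one category would not show in a three-level shift table. If the SAP can no longer be amended before unblinding, its Section 1 allows the same tables as supplementary analyses labelled post hoc.

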8.6.6. Concomitant Medications

All medications taken within 14 days prior to the Screening/Start of Lead-In visit through the end of the follow-up period will be recorded on the Concomitant Medications log. Prior and concomitant medications will be coded using World Health Organization Drug Dictionary Enhanced.

Concomitant medications will include all non-trial medications that are taken on or after administration of study drug. Prior medications will include all non-trial medications that are started prior to the day of administration of the study drug.

The number and percentage of subjects using concomitant medications will be tabulated by Anatomical Therapeutic Chemical (ATC) and PT for all subjects in the SfAS by treatment group. For subject-level analysis, a subject will be counted at most once per ATC and per PT.

Prior and concomitant medication data will also be presented in a data listing for subjects in the SfAS.

8.6.6.1. Imputation Rules for Missing Concomitant Medication Start/Stop Date

Partial and completely missing dates will be imputed for the purposes of classifying concomitant medications as follows:

- Partial dates will be imputed following the same algorithm as for TEAEs.
- For an entirely missing start date (i.e., day, month, and year are missing), the start date will be set to the date of administration of study drug unless the stop date is prior to the date of administration of study drug, in which case the start date will be set to the stop date.

9. OTHER ANALYSES

9.1. Qualitative Questionnaire

This questionnaire records subject experience

9.1.1. Qualitative questionnaire responses

• Analysis of the Endpoint

Responses to the **example to the summarized with** questionnaire will be summarized with frequencies and percentages by item for subjects in the SfAS.

9.2. Tinnitus Functional Index

The Tinnitus Functional Index (Meikle et al 2012) has eight subscales that address the intrusiveness of tinnitus, the sense of control the patient has, cognitive interference, sleep disturbance, auditory issues, relaxation issues, quality of life, and emotional distress. The subject will report answers to each of the 25 questions using a scale of 0-10. The TFI will be given to the subject to complete at the End of Lead-In/Treatment, Day 90, Day 180, and Day 270 visits.

All instrument items, except items 1 and 3, are on an inverted 0-10 scale with 0 being most favorable and 10 being least favorable. Items 1 and 3 are on an inverted 0% to 100% scale with 0% being most favorable and 100% being least favorable. The total score and individual subscale scores are the average item response (all subscales consist of 3 or 4 items) that is then scaled to 0-100. Detailed scoring instructions are in Section 14.3.

No imputation will be performed for missing data and Section 14.3 provides further detail regarding the impact of missing data on TFI scores. No sensitivity analyses will be performed for the TFI endpoints.

9.2.1. Mean total score, individual subscale scores, and loudness score

• Computation of the Endpoint

At each visit, the mean total TFI score and individual subscale scores will be computed per Section 14.3. The loudness score will be the response from item 2.

• Analysis of the Endpoint

The mean total TFI score, individual subscale scores, and loudness score will be summarized descriptively by visit and treatment group for subjects in the FAS.

9.2.2. Change from baseline in mean total score, individual subscale scores, and loudness score

• Computation of the Endpoint

The change from baseline to each post-baseline visit will be computed as w - b where "w" is the post-baseline score and "b" is the score at baseline.

• Analysis of the Endpoint

The change from baseline to each post-baseline visit in mean total TFI score, individual subscale scores, and loudness score will be summarized descriptively by visit and treatment group for subjects in the FAS.

9.3.	Research Assessment on	Quality of Life
	is a PRO questionnaire	
		The subject will complete

the instrument at the End of Lead-In/Treatment and Day 90 visits.

9.3.1. Mean total score, mean domain scores, and individual scores

• Computation of the Endpoint

At each visit, the mean **experiment** score and mean domain scores will be computed per No computation is required for individual scores.

• Analysis of the Endpoint

The mean **score**, mean domain scores, and individual scores will be summarized descriptively by visit and treatment group for subjects in the FAS.

9.3.2. Change from baseline in mean total score, mean domain scores, and individual scores

• Computation of the Endpoint

Page 49 of 64

Using the mean score, mean domain scores, and individual scores

9.4. Speech Reception Threshold (SRT)

Speech reception threshold is being used as a cross-check measure for the results of puretone audiometry. The PTA shall be compared to the SRT to alert the tester to possible concerns about the accuracy of the pure tone results. Left and right ears will be mapped to treated and untreated for analysis.

The qualitative assessment for whether the SRT results suggest hearing thresholds are reliable will be summarized descriptively for treated and untreated ears, separately, for subjects in the SfAS. All data, including the SRT value, will be listed for subjects in the SfAS.

10. INTERIM ANALYSIS AND DATA MONITORING

The blinded data will be continuously monitored for safety throughout the study. No interim analysis is planned.

11. CHANGES TO THE ANALYSES PLANNED IN THE PROTOCOL

Not applicable.

13. APPENDICES

13.1. Study Flow Chart

13.2. Schedule of Assessments

Visit	Screening/ Start of Lead-In	Lead-In Visit	End of Lead-In/ Treatment	In-Clinic Follow-up	In-Clinic Follow up	In-Clinic Follow-up / ET ^e	In-Clinic Observation	In-Clinic Observation	Un-scheduled Visit
Visit Number	1	2	3	4	5	6	7	8	UNS
Assessment/Day	Day -40 to -30	Visit 1 + 16 days	Visit 1 + 35 days	Day 30	Day 60	Day 90	Day 180	Day 270	
Visit Window	N/A	+/- 2 days	+/- 5 days	+/- 5 days	+/- 5 days	+/- 5 days	+/- 7 days	+/- 7 days	N/A
Informed Consent	X								
Inclusion/ Exclusion Criteria	X ^a	Xa	Хр						
Eligibility Assessment by EDC	X	X	Хр						
Demographics	Xª								
Medical History	Xª	X ^a	Хр						
Concomitant Medication	Xª	Xª	X ^{b, c}	Х	Х	X	Х	Х	Х
Physical Examination including weight and height	X								X ^d
Vital Signs (body temperature, pulse rate, bp)	Х	X	Хр	Х	Х	X			X ^d
Tympanometry	Х		Хр	Х	Х	X	Х	Х	X ^d
Standard Pure Tone Audiometry	Х	X	Xb	Х	Х	X	Х	Х	X ^d
Speech Reception Threshold (SRT)	Х	Х	Х	Х	Х	X	Х	Х	X ^d
Extended High Frequency Audiometry	X	Х	Хр	Х	Х	Х	Х	Х	X ^d
Word recognition, quiet (Maryland CNC)	X	X	Xb	Х	Х	X	Х	Х	X ^d
Word recognition (W-22)	Х	Х	Хр	Х	Х	X	Х	Х	X ^d
Words in noise (WIN)	Х	Х	Хр	Х	Х	X	Х	Х	X ^d
Tinnitus Functional Index	Ī		Xb			X	Х	Х	X ^d

Page 53 of 64

Version Date: 2023-01-19

Statistical Analysis Plan 19 January 2023

Visit	Screening/ Start of Lead-In	Lead-In Visit	End of Lead-In/ Treatment	In-Clinic Follow-up	In-Clinic Follow up	In-Clinic Follow-up / ET ^e	In-Clinic Observation	In-Clinic Observation	Un-scheduled Visit
Visit Number	1	2	3	4	5	6	7	8	UNS
Assessment/Day	Day -40 to -30	Visit 1 + 16 days	Visit 1 + 35 days	Day 30	Day 60	Day 90	Day 180	Day 270	
Visit Window	N/A	+/- 2 days	+/- 5 days	+/- 5 days	+/- 5 days	+/- 5 days	+/- 7 days	+/- 7 days	N/A
Qualitative									
Columbia Suicide Severity Rating Scale			Хр	Х	Х	X	Х	Х	X ^d
PGI-S Hearing Loss Scale			Хр						
PGI-S Daily Impacts Scale			Xb						
PGI-C Hearing Loss Scale						X			
PGI-C Daily Impacts Scale						X			
Otoscopy	X		Хр	X	Х	X	X	X	X ^d
Urine Pregnancy Test (women of childbearing potential only)	Х		Хр			Х			X ^d
Randomization by EDC			Хр						
Study Medication (FX-322 or placebo)			Х						
Adverse Events			X¢	Х	Х	Х	Х	Х	Х

a- Performed during the Screening Visit and again if a subject notes a change in their medical status during the lead in period

b – Assessment performed prior to injection

c- Assessments performed after injection

d- Perform at Investigator Discretion

e- If a subject discontinues prior to Visit 6 (Day 90), all efforts should be made to complete the Visit 6 (Day 90) In-Clinic Follow-up/Early Termination (ET) Visit as soon as possible and, whenever possible, prior to starting any new medication or treatment.

Page 54 of 64

14. ATTACHMENTS

14.1. Thornton and Raffin (1978) Word Recognition Scoring Chart

TABLE 4. Lower and upper limits of the 95% critical differences for percentage scores. Values within the range shown are not significantly different from the value shown in the percentage Score columns (p > 0.05).

% Score	n = 50	n = 25	n = 10	% Score	n = 100°
0	0-4	0-8	0-20	50	37-63
2	0-10			51	38-64
4	0-14	0-20		52	39-65
6	2-18			53	40-66
8	2-22	0-28		54	41-67
10	2-24	0.20	0-50	55	42-68
12	4-26	4-32	0-00	56	43-69
14	4-30	4-04		57	44-70
16	6-32	4-40		58	45-71
18	6-34	4-40		59	46-72
20			0.00		
	8-36	4-44	0-60	60	47-73
22	8-40	0.40		61	48-74
24	10-42	8-48		62	49-74
26	12-44			63	50-75
28	14-46	8-52		64	51-76
30	14-48		10-70	65	52-77
32	16-50	12-56		66	53-78
34	18-52			67	54-79
36	20-54	16-60		68	55-80
38	22-56			69	56 - 81
40	22-58	16-64	10-80	70	57-81
42	24-60			71	58 - 82
44	26-62	20-68		72	59-83
46	28-64			73	60-84
48	30-66	24 - 72		74	61-85
50	32-68		10-90	75	63-86
52	34-70	28-76	20 00	76	64-86
54	36-72	2010		77	65-87
56	38-74	32-80		78	66-88
58	40-76	02-00		79	67-89
60	42-78	36-84	20-90	80	68-89
62	44-78	00-04	20-50	81	69-90
64		40.84			71-91
66	46-80 48-82	40-84		82 83	72-92
68		44.90			
70	50-84	44-88	20.00	84	73-92
70	52-86	49.00	30-90	85	74-93
	54-86	48 - 92		86	75-94
74	56-88	50.00		87	77-94
76	58-90	52 - 92		88	78-95
78	60-92	K0.00	10 100	89	79-96
80	64-92	56-96	40-100	90	81-96
82	66-94			91	82-97
84	68-94	60-96		92	83-98
86	70-96			93	85-98
88	74-96	68-96	-	94	86-99
90	76-98		50-100	95	88-99
92	78-98	72 - 100		96	89-99
94	82-98			97	91-100
96	86-100	80-100		98	92-100
98	90-100			99	94-100
100	96-100	92-100	80-100	100	97-100

°If score is less than 50%, find % Score = 100-observed score and subtract each critical difference limit from 100.

14.2. Carney-Schlauch (2007) Word Recognition Scoring Chart

% score	n = 50	n = 25	n= 10	% score	n = 100	% score	n = 100
0	0-6	0-12	0-20	50	37-63	50	37-63
2	0-10			49	36-62	51	38-64
4	0-14	0-20		48	35-61	52	39-65
6	0-18			47	34-60	53	40-66
8	2-20	0-28		46	33-59	54	41-67
10	2-24		0-40	45	32-58	55	42-68
12	4-26	0-32		44	31-57	56	43-69
14	4-28	 		43	30-56	57	44-70
16	6-32	4-40		42	29-55	58	45-71
18	6-34			41	28-54	59	46-72
20	8-36	4-44	0-50	40	28-53	60	47-72
22	10-38			39	27-52	61	48-73
24	10-42	8-48		38	26-51	62	49-74
26	12-44			37	25-50	63	50-75
28	14-46	8-52		36	24-49	64	51-76
30	16-48		10-70	35	23-48	65	52-77
32	16-50	12-56		34	22-47	66	53-78
34	18-52			33	23-46	67	54-79
36	20-54	16-60		32	20-45	68	55-80
38	22-56			31	20-44	69	56-80
40	24-58	16-64	10- 70	30	19-43	70	57-81
42	24-60			29	18-42	71	58-82
44	26-62	20-68		28	17-41	72	59-83
46	28-64			27	16-39	73	61-84
48	30-66	24-72		26	15-38	74	62-85
50	32-68		20-80	25	15-37	75	63-85
52	34-70	28-76		24	14-36	76	64-86
54	36-72	20 / 0		23	13-35	77	65-87
56	38-74	32-80		22	12-34	78	66-88
58	40-76	02 00		21	11-31	79	69-89
60	42-76	36-84	30 -90	20	11-32	80	68-89
62	44-78	00 04		19	10-30	81	70-90
64	46-80	40-84		18	9-29	82	71-91
66	48-82			17	8-28	83	72-92
68	50-84	44-88		16	8-27	84	73-92
70	52-84		30-90	15	7-26	85	74-93
72	54-86	48-92		14	6-24	86	76-94
74	56-88			13	6-23	87	77-94
76	58-90	52-92		12	5-22	88	78-95
78	62-90			11	4-21	89	79-96
80	64-92	56-96	50 -100	10	4-19	90	81-96
82	66-94			9	3-18	91	82-97
84	68-94	60-96		8	3-17	92	83- 97
86	72-96			7	2-15	93	85-98
88	74-96	68-100		6	1-14	94	86-99
90	76-98		60 -100	5	1-12	95	88-99
92	80-98	72-100		4	1-11	96	89-99
94	82-100			3	0-9	97	91-100
96	86-100	80-100		2	0-7	98	93-100
98	90-100	00 100		1	0-6	99	94-100
100	94-100	88-100	80-100	ò	0-3	100	97-100

Table 1. Limits (upper and lower) of 95% critical differences for percent scores on lists of length n = 10, 25, 50, and 100.

Note. The upper and lower scores in the 95% critical interval are shown for various list sizes. Scores on successive administrations of a word recognition test may be considered to be "significantly different," at the .05 level, if they exceed the upper limit or fall below the lower limit. Discrepancies between these simulated values and those in Thornton and Raffin (1978) are coded as follows: numerals in boldface indicate that the critical interval is narrower on that side than in the previous table; underlined numerals indicate that the critical interval is wider on that side than in the previous table.

